The diaries of the participants (study groups and control groups) are presented in Appendices 1 and 2. The diaries include 2 blocks to be filled in by the research participant: 1) initial information about the participant: initials, gender, date of birth, presence of smoking experience; 2) information about compliance with the accepted therapy, about the tolerability of preventive therapy, cases of ARVI incidence, severity and duration of symptoms, treatment methods.

To reduce the risk of violation of the dosage regimen, participant diary in the study group provides detailed instructions on the preparation, administration and features of the use of the drug under study, as well as the diary will contain a calendar for registering the days of

instillations. In addition, when issuing a diary to a participant, it indicates the contact details of the doctor for direct communication with the researcher in case of symptoms of acute respiratory viral infections during the study period.

Nasopharyngeal smear

Prior to the start of preventive observation, the participant must take a smear from the mucous membranes of the upper respiratory tract (nasopharyngeal⁸). It is allowed to use the results of a PCR test before inclusion in the study, but no later than 3 days. If the study is completed with the registration of a confirmed case of COVID-19, PCR test is not performed at visit 3, the results of the tests performed to confirm the patient's recovery are accepted.

The procedure for working with biological material:

1. The biomaterial is taken on an empty stomach or not earlier than 2 hours after eating and drinking; before rinsing, irrigation with medicines.
2. The study is conducted before the start of treatment with antibiotics, antiseptics, antifungal and antiviral drugs.
3. Caution should be exercised in the presence of pronounced inflammatory processes in the pharynx. In case of severe edema, the material is not taken.
4. The material is taken before carrying out hygienic procedures.

Taking a nasopharyngeal smear for the presence of SARS-CoV-2 RNA is carried out as follows:

1. Scraping of epithelial cells from the oropharynx is carried out with a dry probe, rotational movements from the surface of the tonsils, palatine arches and posterior wall of the oropharynx.

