Address of the place of manufacture: [name], J.S.C. "Biomed"-Mechnikov Tel/[contact], [name]

E-mail: [contact] Internet: www.pharmaclon.ru

Labelling: The inscription "For post-marketing research RAIN-2020" is applied to the primary packaging and secondary (consumer) packaging of the study drug product, the inscription "Not for sale" is additionally applied to the secondary (consumer) packaging in accordance with the requirements of the Federal Law "On Circulation of Medicines" dated 12.04.2010 N 61-FZ as amended Federal Law No. 429-FZ from 22.12.2014.

Compliance assessment

Assessment of compliance with study preventive therapy is evaluated on the basis of data recorded in the participant's diary, on visit 3, as well as in advance as part of an oral survey of the participant on a phone call visit after the end of preventive use of the drug. Compliance is assessed on a 100% scale, where:

100% – participant completed 2 cycles of 10-day courses without violating the dosage regimen and the frequency of admission

90% – participant completed 2 cycles of 10-day courses with a single violation of dosage regimen or dosage frequency

80% – participant completed 1 cycle of the 10-day course without violating dosage regimen or dosage frequency

70% – participant completed 2 cycles of 10-day courses with a double violation of dosage regimen or dosage frequency (single violation of each course)

60% – participant completed 1 cycle of 10-day course with a single violation of dosage regimen or dosage frequency

50% or less – participant completed 1 or 2 cycles of 10-day courses with a systematic (twofold or more) violation of the dosage regimen or dosage frequency in each of the courses (non-compliance with a single dose, frequency of use and/or its duration).

Compliance of 50% or less is the criterion for excluding a participant from the study.

STUDY PARAMETERS OF EFFICIENCY AND SAFETY

Effectiveness criteria

Effectiveness criteria will be evaluated according to the data recorded in the participants' diaries, in primary medical documentation.

Primary effectiveness criterion:

The proportion of patients with acute respiratory viral infections, including COVID-19, at the end of the period of preventive administration of the drug (measurement time: 28 days).

Secondary effectiveness criterion:

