1. The proportion of patients with confirmed COVID-19 at the end of the period of preventive treatment of the drug (measurement period: 28 days).
2. The proportion of patients with acute respiratory viral infections, including COVID-19, at the end of the follow-up period (change period: 2 months).
3. The proportion of patients with confirmed COVID-19 at the end of the follow-up period (change period: 2 months).
4. Frequency of development of complicated course of ARVI.
5. The proportion of participants with each of the scores (0-8) according to the WHO Clinical Improvement Scale (change period: 28 days).
6. The proportion of participants with each of the scores (0-8) according to the WHO Clinical Improvement Scale (change period: 2 months).
7. Duration of symptoms of the disease of study participants who had acute respiratory viral infections, including COVID-19 (change period: 2 months).
8. The duration of the symptoms of the disease of the study participants who were infected with ARVI, including COVID-19 (measurement period: 28 days).

Confirmation of clinical cases of ARVI, including COVID-19:

In the following cases:

- 1) a positive result of PCR on SARS-CoV-2 RNA, regardless of the presence of clinical symptoms;
- 2) appearance of clinical symptoms of ARVI in the absence of a PCR result on SARS-CoV-2 RNA or in the case of a negative result on SARS-CoV-2 RNA, -

at any stage during participation in the study, a completion visit (Visit 3) is conducted at the end of the quarantine period (at least 14 days from the date of signing Consent for the treatment of a new COVID-19 coronavirus infection in outpatient settings (at home) and compliance with the isolation regime or discharge from the hospital in case of laboratory confirmation of COVID-19), at which the patient returns the participant's diary and reports his condition to the doctor-researcher, transmits information about hospitalization, duration of symptoms, results of tests and performed studies.

Definition of the COVID-19 case:

Suspicious case of COVID-19

Body temperature above 37.5° in addition to one or more of the following signs (in the absence of other known causes that explain the clinical picture, regardless of the epidemiological history):

- Cough (dry or with scant sputum)
- Shortness of breath
- Feeling of congestion in the chest
- SpO₂ no more than 95%
- Sore throat
- Nasal stuffiness or moderate rhinorrhea
- Smell disorders or anosmia
- Ageusia
- Conjunctivitis
- Fatigue

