|---------------------------------|---|

Administration of study drug

Time of administration: | ____ :| ____ |

In case of complaints, symptoms of ARVI, please fill out the table below:

| Start date | End date | Complaints | Therapy (if taken) |
|------------|----------|------------|--------------------|
| | | | |
| | | | |
| | | | |
| | | | |

| | |
|---------------------------------|--|
| Course 1 Day 2 | Date ____ ____ ____ ____ ____ day month year |
|---------------------------------|--|

In case of complaints, symptoms of ARVI, please fill out the table below:

| Start date | End date | Complaints | Therapy (if taken) |
|------------|----------|------------|--------------------|
| | | | |
| | | | |
| | | | |
| | | | |

| | |
|---------------------------------|--|
| Course 1 Day 3 | Date ____ ____ ____ ____ ____ day month year |
|---------------------------------|--|

Time of administration: | ____ :| ____ |

In case of complaints, symptoms of ARVI, please fill out the table below:

| Start date | End date | Complaints | Therapy (if taken) |
|------------|----------|------------|--------------------|
| | | | |
| | | | |
| | | | |
| | | | |

| | |
|---------------------------------|--|
| Course 1 Day 4 | Date ____ ____ ____ ____ ____ day month year |
|---------------------------------|--|

In case of complaints, symptoms of ARVI, please fill out the table below:

| Start date | End date | Complaints | Therapy (if taken) |
|------------|----------|------------|--------------------|
| | | | |
| | | | |
| | | | |
| | | | |

| | |
|---------------------------------|--|
| Course 1 Day 5 | Date ____ ____ ____ ____ ____ day month year |
|---------------------------------|--|

Time of administration: | ____ :| ____ |

In case of complaints, symptoms of ARVI, please fill out the table below:

| Start date | End date | Complaints | Therapy (if taken) |
|------------|----------|------------|--------------------|
| | | | |
| | | | |
| | | | |
| | | | |

| | |
|-----------------|--|
| Course 1 | Date ____ ____ ____ ____ ____ |
|-----------------|--|

| | |
|--------------|----------------|
| Day 6 | day month year |
|--------------|----------------|

In case of complaints, symptoms of ARVI, please fill out the table below:

| Start date | End date | Complaints | Therapy (if taken) |
|------------|----------|------------|--------------------|
| | | | |
| | | | |
| | | | |

| | |
|---------------------------------|--|

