Research participant's diary

Protocol of post-marketing non-interventional study

"A prospective randomized open-label comparative study of the use of the intranasal form of human recombinant interferon gamma for the prevention of acute respiratory viral infections, including diseases caused by coronavirus infection 2019 (COVID-19)"

RAIN-2020

Control Group

Participant screening number: |__|_|__|_|__|_|

Randomization number of the participant: |__|_|__|_|__|_|

Date of signing informed consent: |__|_|__|_|__|_|__|_|__|_|

day month year

The start date for the diary: |__|_|__|_|__|_|__|_|__|_|
day month year

The end date for the diary: |__|_|__|_|__|_|__|_|
day month year

Participant's signature _____

Signature of the medical researcher _____

| Participant _____ (randomization number) | Initial data | Date __ _ __ _ __ _ day month year |
|---|--------------|---|
|---|--------------|---|

| | | |
|---------------------|------------------------------------|----|
| 1. Initials | | |
| 2. Date of birth | | |
| 3. Gender | male / female | |
| 4. Smoking, history | yes (____ pack/day for ____ years) | no |

The observation period is 2 months

If you are taking medications to prevent ARVI, please fill out the table below:

| | |
|---|---------------------------|
| Participant _____ (randomization number) | Observation period |
| Participant _____ (randomization number) | Observation period |

In case of complaints, symptoms of ARVI, please fill out the table below:

¹⁶ Before using the drug, it is necessary to familiarize yourself with the current instructions for medical use to exclude contraindications.

¹⁷ A single dose and the frequency of dosing are indicated

| | | | |
|--|--|--|--|
| | | | |
| | | | |
| | | | |
| | | | |
| | | | |
| | | | |
| | | | |

Appendix 3

Form for reporting unlabeled serious adverse reaction

Reporting of unlabeled serious reaction to a drug being studied in a clinical trial

| | | | | | |
|---|--|--|--|--|--|
| Research protocol No. | | | | | |
| Name of the research protocol | | | | | |
| Name of study drug | | | | | |
| Study phase | | | | | |
| The name of the medical institution in which the SAE was detected | | | | | |

Information about the SAE

| | | | | | |
|--|------------------|--------|-----------|--------------------------|--|
| 1. Initials of the patient | 2. Date of birth | 3. Age | 4. Gender | 5. Start date of the SAE | 6. Mark everything that corresponds to the SAE |

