3.2. Registration, analysis and evaluation of effectiveness parameters

The effectiveness will be evaluated based on the data obtained during the study visits. The effectiveness assessment will include the presence of a case of ARVI, including COVID-19.

Confirmation of clinical cases of ARVI, including COVID-19:

In the following cases:

- 1) a positive result of PCR on SARS-CoV-2 RNA, regardless of the presence of clinical symptoms;
- 2) appearance of clinical symptoms of ARVI in the absence of a PCR result on SARS-CoV-2 RNA or in the case of a negative result on SARS-CoV-2 RNA, -

at any stage during participation in the study, a completion visit (Visit 3) is conducted at the end of the quarantine period (at least 14 days from the date of signing Consent for the treatment of a new COVID-19 coronavirus infection in

outpatient settings (at home) and compliance with the isolation regime or discharge from the hospital in case of laboratory confirmation of COVID-19), at which the patient returns the participant's diary and reports his condition to the doctor-researcher, transmits information about hospitalization, duration of symptoms, results of tests and performed studies.

Definition of the COVID-19 case:

Suspicious case of COVID-19

Body temperature above 37.5 ° in addition to one or more of the following signs (in the absence of other known causes that explain the clinical picture, regardless of the epidemiological history):

- Cough (dry or with scant sputum)
- Shortness of breath
- Feeling of congestion in the chest
- SpO₂ no more than 95%
- Sore throat
- Nasal stuffiness or moderate rhinorrhea
- Smell disorders or anosmia
- Ageusia
- Conjunctivitis
- Fatigue
- Myalgia
- Headache
- Vomiting
- Diarrhea
- Skin rash

Probable case of COVID-19

Body temperature above 37.5° in addition to one or more of the following signs:

- Cough (dry or with scant sputum)
- Shortness of breath
- Feeling of congestion in the chest
- SpO₂ no more than 95%
- Sore throat
- Nasal stuffiness or moderate rhinorrhea
- Smell disorders or anosmia
- Ageusia
- Conjunctivitis
- Fatigue
- Myalgia
- Headache
- Vomiting
- Diarrhea
- Skin rash

In the presence of at least one of the epidemiological signs:

- Return from cross-border travel 14 days before the onset of symptoms

- The presence of close contacts over the past 14 days with a person under surveillance for COVID-19, who subsequently became ill

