Analysis of the source data

Demographic characteristics, baseline, and follow-up characteristics such as anamnesis, comorbidities and medications used will be described by treatment groups for the ITT population and then safety, if they differ.

⁶ URL <https://www.R-project.org/>

⁷ <https://www.r-project.org/doc/R-FDA.pdf>

Primary Endpoint Analysis

The main parameter of the effectiveness of the preventive use of Ingaron® is the proportion of patients with acute respiratory viral infections, including COVID-19, at the end of the period of preventive administration of the drug (measurement time: 28 days).

In accordance with the purpose and objectives of the study, the null and alternative hypotheses are formulated as follows:

- Null hypothesis (H_0) consists in the assumption that the prophylactic administration of Ingaron will not lead to a change in the incidence of acute respiratory viral infections, including COVID-19, among adult volunteers;
- Alternative hypothesis (H_a) is that in the study group, the proportion of ARVI cases, including COVID-19, will differ from the control group.

$$H_0: \mu_1 = \mu_2$$

$$H_a: \mu_1 \neq \mu_2,$$

where μ is the fraction of the main variable for the corresponding group.

To test these hypotheses, the method of a two-way variant of the Fisher's exact test (with expected frequencies less than 5) or the Pearson's chi-squared test (χ^2) (with the Yates correction for expected frequencies more than 5, but less than 10) will be used.

In all cases, the significance level (α is the probability of an error of the first kind) 0.05 will be used.

The analysis of the primary efficiency parameter will be carried out on the ITT population (main analysis), as well as – additionally – on the PP population (additional analysis).

Data on the case of ARVI (COVID-19) is collected during the entire study by filling out a form on the registration of a case of ARVI.

Secondary Endpoint analysis

The following secondary efficacy parameters in this study are quantitative indicators that will be compared between treatment groups:

- proportion of patients with confirmed COVID-19 at the end of the period of preventive administration of the drug (measurement period: 28 days);
- proportion of patients with acute respiratory viral infections, including COVID-19, at the end of the observation period (change period: 2 months);
- percentage of patients with confirmed COVID-19 at the end of the follow-up period (change period: 2 months);

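### The readable Group I diary has no page, prompt or instruction for symptoms in the break or after Course 2 Day 9, while the Group II diary covers 2 months, so written symptom prompting differs by arm

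*Protocol*

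**What the plan says.** The protocol section on participant diaries describes one content list for both groups, which includes "cases of ARVI incidence, severity and duration of symptoms, treatment methods". Under Effectiveness criteria it names the sources: "Effectiveness criteria will be evaluated according to the data recorded in the participants' diaries, in primary medical documentation". The schedule of procedures has the diary returned at Visit 3.

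**Group I diary (Appendix 1).** There is one page for each of Course 1 Days 1-9 and Course 2 Days 1-9. Each page has the same symptom prompt and a blank table headed "Start date | End date | Complaints | Therapy (if taken". After the Course 2 Day 9 table the next text is Appendix 2.

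**Group II diary (Appendix 2).** It states "The observation period is 2 months" and prompts for preventive medicines. Under an observation-period heading it then prompts for complaints and ARVI symptoms. The symptom prompt is not tied to any study day.

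**Sources common to both arms.** SAP section 3.2 says "The effectiveness will be evaluated based on the data obtained during the study visits". SAP section 5.1 says that information on an ARVI case "is collected during the entire study by filling out a form on the registration of a case of ARVI". After a case, the protocol provides a completion visit at which the participant "transmits information about hospitalization, duration of symptoms, results of tests and performed studies".

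**The concern.** The trial is open-label, and the case definition includes "appearance of clinical symptoms of ARVI in the absence of a PCR result on SARS-CoV-2 RNA or in the case of a negative result". A symptomatic illness can therefore count without laboratory confirmation, so case capture depends partly on what participants notice, write down and report. Symptom duration needs a start and an end date, which are best recorded when they occur.

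If the two arms are prompted to write at different times and with different frequency, a difference in recorded illness can arise from the form rather than from the drug. SAP section 2.1 says that all participants follow the same visits and procedures, and neither document explains why the diaries should differ in the period they cover. The endpoints most exposed are the 2-month ARVI proportion and the 2-month symptom duration. Confirmed COVID-19 rests on laboratory results and depends less on the diary.

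**Working it through.** **Inputs**
- Preventive course: 10 + 7 + 10 days (Protocol, Randomization of study participants).
- Group I pages: Days 1-9 of each course (Appendix 1).
- Participation: 56-62 days (Protocol, Main stages of the study).
- Assumption: the first instillation is on study day 1. Counting it as day 0 moves every position below by one day.

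**Step 1. Reproduce the plan's figure.** 10 + 7 + 10 = 27 days, as the protocol states.

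**Step 2. Place the last Group I page.** Course 2 Day 9 = 10 + 7 + 9 = study day 26.

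**Step 3. Count the days after it.** To day 56: 56 - 26 = 30 days (30/56 = 54%). To day 62: 62 - 26 = 36 days (36/62 = 58%).

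**Step 4. Count the gap between courses.** Course 1 Day 10 is study day 10 and the break is days 11-17, so 1 + 7 = 8 days have no page of their own.

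**Step 5. Look at the 28-day window.** Days 10-17, 27 and 28 have no page of their own: 8 + 2 = 10 of 28 days. For days 10-17, nine Course 2 pages follow, so an illness starting in the break can still be entered under a later date. Only days 27-28 have no later page.

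**Step 6. Compare the prompts.**

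| Period | Group I diary (readable text) | Group II diary (readable text) |
|---|---|---|
| Course days with a page | 9 + 9 = 18 daily symptom prompts | One undated prompt for the 2 months |
| Day 10 and the 7-day break | No page, prompt or instruction | Same undated prompt |
| After Course 2 Day 9 | No page, prompt or instruction | Same undated prompt |

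**Step 7. Time without scheduled contact.** On the day ranges in the Main stages list, Visit 2 (a telephone call) is at day 28-30 and Visit 3 at day 56-62. The interval is 56 - 30 = 26 to 62 - 28 = 34 days, roughly four to five weeks. Only Group II has a written prompt that covers it.

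The documents give no rate at which unprompted illness goes unrecorded in either arm, so no bias can be calculated from them.

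**The case against.** The strongest reply is that cases are captured elsewhere, and equally. Complaints and effectiveness are assessed at Visits 2 and 3 in both arms. The ARVI case form runs throughout the study. A known case leads to a completion visit that collects symptom duration. The diary carries the doctor's contact details, and primary medical records are an effectiveness source. This stands as a real limit on the effect, but it does not remove the difference. The completion visit follows a case that is already known, the contact details rely on the participant calling, and the SAP does not say how an illness first reaches the case form. Between Visits 2 and 3 these routes rest largely on recall or on the participant volunteering the illness.

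A reader might infer that Group I has nowhere in the diary to write a follow-up illness. The documents do not support that. The Group I tables have free start and end dates and blank rows, and the diary is kept until Visit 3, so a late illness could be written on an existing page. What is missing is a dedicated page and any instruction to do so.

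A reader might also infer that Group I illness is under-recorded and that the drug is thereby favoured. That looks at one half of the asymmetry. Eighteen daily prompts in Group I against one readable prompt in Group II could raise Group I recording during the courses.

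Finally, the readable text is imperfect. The opening of Appendix 1 and the tables of Appendix 2 are damaged: the number, layout and headings of the Group II tables cannot be established, and a lost Group I page cannot be excluded. Against a lost page, all 18 daily pages survive in order, and no missing-figure mark stands between Course 2 Day 9 and Appendix 2.

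**Conclusion.** The point holds as an avoidable difference in recording forms, with medium confidence. In the readable text, Group I has no dedicated symptom page, prompt or instruction on Day 10 and the 7-day break, or for the last 30-36 of 56-62 days. Group II has a prompt for the whole 2 months. Group I is prompted more often during the courses. Prompting therefore differs by arm in both periods, and neither the direction nor the size of any bias can be determined.

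The relevance is mainly to the 2-month ARVI and symptom-duration endpoints. The documents do not support a claim that the 28-day primary endpoint is compromised. Illness in the break can be entered on later pages, only days 27-28 have no later page, and the visits ask both arms about complaints. This is a low-cost improvement worth considering, not a demonstrated bias. It rests on the readable diaries being complete and on counting the first dose as study day 1.

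**What to change.** First compare the printed diaries with the readable appendices, to confirm that Group I has no follow-up page and to see the Group II tables as issued.

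If the difference is confirmed:
- Use one identical dated symptom log in both arms from randomisation to Visit 3.
- Make the Group I dosing pages a separate insert.
- Instruct participants in both arms to enter illness on any day, including the break and follow-up.
- State in the SAP that day-28 status is classified by date of symptom onset.

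The diary change is one of layout and adds a little length. The classification rule is one sentence in the SAP. No visit, endpoint or sample size changes. If diaries have already been issued, the report should describe the difference and say which source supplied each ARVI case.
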